### **Withdrawal From the Study**

A subject will be withdrawn from the study for any of the following reasons:

- Lost to follow-up.
- Withdrawal of consent.
- Death.

If a subject discontinues study treatment before the end of the 24-week treatment phase or the 24-week treatment extension phase, follow-up assessments should be obtained until 24 weeks after EOT (Schedule 1) unless the subject withdraws consent.

If a subject withdraws before completing the study, the reason for withdrawal is to be documented in the eCRF and in the source document. Subjects who withdraw consent will be offered an optional safety follow-up visit. Study treatment assigned to the withdrawn subject may not be assigned to another subject. Subjects who withdraw will not be replaced.

If a subject is lost to follow-up, every reasonable effort must be made by the study-site personnel to contact the subject and determine the reason for discontinuation/withdrawal. The measures taken to follow up must be documented.

### **10.3. Withdrawal From the Use of Research Samples**

A subject who withdraws from the study will have the following options regarding the pharmacogenomics (host DNA) research samples:

- The collected samples will be retained and used in accordance with the subject's original separate informed consent for pharmacogenomics (host DNA) research.

- The subject may withdraw consent for pharmacogenomics (host DNA) research, in which case the samples will be destroyed and no further testing will take place. To initiate the sample destruction process, the investigator must notify the sponsor study-site contact of withdrawal of consent for the pharmacogenomics (host DNA) research and to request sample destruction. The sponsor study-site contact will, in turn, contact the biomarker representative to execute sample destruction. If requested, the investigator will receive written confirmation from the sponsor that the samples have been destroyed.

### **Withdrawal From the Optional Research Samples While Remaining in the Main Study**

The subject may withdraw consent for pharmacogenomics (host DNA) research while remaining in the study. In such a case, the pharmacogenomics (host DNA) research samples will be destroyed. The sample destruction process will proceed as described above.

### **Withdrawal From the Use of Samples in Future Research**

The subject may withdraw consent for use of samples for research (refer to Section 16.2.5). In such a case, samples will be destroyed after they are no longer needed for the clinical study. Details of the sample retention for research are presented in the main ICF and in the separate ICF for pharmacogenomics (host DNA) research.

## **11. STATISTICAL METHODS**

Statistical analysis will be done by the sponsor or under the authority of the sponsor. A general description of the statistical methods to be used to analyze the efficacy and safety data is outlined below. Specific details will be provided in the SAP.

### **11.1. Subject Information**

For all subjects who receive at least 1 dose of study drug descriptive statistics will be provided.

All demographic (eg, age, length, weight, race, gender) and other initial subject characteristics (eg, physical examination, medical and surgical history, family history, concomitant diseases) will be tabulated and analyzed descriptively by study treatment.

### **11.2. Sample Size Determination**

As this is an exploratory, hypothesis-generating study, no formal statistical hypothesis testing will be performed.

The adequacy of the sample size for the different parts of the study has been assessed by evaluating the performance of the planned analyses on the primary endpoint (mean HBsAg change from baseline at Week 24) comparing JNJ-56136379+NA with placebo+NA as outlined in Section 11.3. Baseline is defined as the last assessment prior to the first intake of study drugs (JNJ-56136379/NA/placebo) on Day 1.

Power was assessed using simulations (10,000 replicates per scenario) with means and SDs for the placebo+NA and JNJ-56136379+NA arms as listed in Table 7. Mean and SD may depend on HBeAg status at baseline and prior treatment (currently not being treated or virologically

suppressed). Treatment with JNJ-56136379 was set to result in one additional mean  $\log_{10}$  IU/mL decline in HBsAg from baseline at Week 24. Data were simulated from mixture distributions which reflect the skewed distributions which are typical HBsAg decline data. It is assumed that HBeAg-positive subjects will enroll slower than HBeAg-negative subjects, particularly in virologically suppressed subjects. Therefore, the aim is to have at least 40% HBeAg-positive subjects currently not being treated and 30% HBeAg-positive virologically suppressed subjects.

For the dose-response modeling (multiple contrast test) the placebo+NA arms of Parts A and B will be pooled and the HBeAg subgroups will be pooled per dose. Assuming the treatment effect does not depend on HBeAg status, the power to detect a dose-response signal ( $\alpha=0.10$ , one-sided) depends on the assumed effect of the low dose: ranging from 91% when the low dose has no effect to 99% when the low dose has the same effect as the high dose. Sensitivity analyses will be done investigating differences across Parts A and B and differences between the two HBeAg subgroups.

A Bayesian analysis will be conducted for Part A and Part B separately to compare the mean HBsAg change from baseline at Week 24 of JNJ-56136379 as monotherapy and in combination with NA versus placebo+NA by HBeAg subgroup. This Bayesian analysis will incorporate historical data for the placebo+NA arm(s) in an informative meta-analytic predictive (MAP) prior with robustness modifier. For the current sample size simulations, historical data comes from an ongoing systematic literature review on HBsAg declines during NA treatment, resulting in 20 studies including around 2,835 subjects. More details on the eventual historical data, including all references to all studies, will be provided in the Modeling and Simulation Report/SAP. The Bayesian equivalent of power, ie, the likelihood that the posterior probability that the mean change from baseline of HBsAg at Week 24 is larger in the JNJ-56136379+NA arm than in the placebo+NA arm is at least 90%, was determined. The results are summarized in [Table 7](#).

It is concluded that, under the assumptions made, the posterior distribution of the estimate of treatment difference between the placebo+NA and JNJ-56136379+NA arm will be precise enough to allow meaningful conclusions. The probability to detect a treatment effect with at least 90% confidence is 0.80 or higher for the HBeAg-negative subgroup in both subjects currently not being treated and virologically suppressed subjects. For the HBeAg-positive subgroup, power is substantially lower which increases the risk of inconclusive results. However, if the interim analysis at Week 12, Week 24 or Week 48 indicates no safety concerns and a potential benefit, a moderate sample size increase for HBeAg-positive subjects to a maximum of 6 subjects on placebo+NA and 18 subjects on JNJ-56136379 monotherapy and JNJ-56136379+NA per study part may be considered. This will increase the probability to detect a treatment effect in these subgroups from 64% or 57% to around 84%.

**Table 7: Bayesian Power Analysis for the Different Prior Treatment and HBeAg Status Subgroups: HBsAg Change From Baseline**

	HBeAg Status	HBsAg ( $\log_{10}$ IU/mL) Change From Baseline		Sample Size (Placebo+NA/JNJ-56136379+NA)	Power a
		Mean $\pm$ SD	Mean $\pm$ SD		
		Placebo+NA	JNJ-56136379+NA		
Currently not being treated	Positive	-0.35 $\pm$ 0.6	-1.35 $\pm$ 2.16	4/12 b	0.64
	Negative	-0.05 $\pm$ 0.4	-1.05 $\pm$ 2.16	6/18 b	0.84
Virologically suppressed	Positive	-0.05 $\pm$ 0.4	-1.05 $\pm$ 2.16	3/9 c	0.57
	Negative	-0.05 $\pm$ 0.4	-1.05 $\pm$ 2.16	7/21 c	0.89

a The probability to conclude that the difference in Week 24 HBsAg change from baseline between JNJ-56136379+NA and placebo+NA is larger than 0 with 90% confidence

b Expected sample size when 40% of the subjects are HBeAg-positive

c Expected sample size when 30% of the subjects are HBeAg-positive

### 11.3. Efficacy Analyses

All subjects who received at least 1 dose of study drug and were randomized will be included in the efficacy analysis.

The main comparisons of interest in the efficacy analyses are:

- to evaluate the efficacy of 24 weeks of JNJ-56136379 monotherapy versus placebo+NA;
- to evaluate the efficacy of 24 weeks of JNJ-56136379+NA versus placebo+NA;
- to evaluate the efficacy of 24 weeks of JNJ-56136379 monotherapy versus JNJ-56136379+NA.

These comparisons will be done overall, by subject population (ie, subjects currently not being treated or virologically suppressed by current NA treatment), and by HBeAg status. Additionally, the JNJ-56136379 dose-response relation will be evaluated.

The primary endpoint for these efficacy comparisons is the change from baseline in HBsAg levels, while additional virological and serologic markers will also be assessed in these comparisons as secondary and exploratory efficacy objectives.

#### 11.3.1. Analysis of Primary Endpoint (Change From Baseline in HBsAg Levels at Week 24)

Within Part A and Part B, the magnitude of the effect of JNJ-56136379+NA as compared to placebo+NA will be evaluated using the posterior distribution of the treatment effect (difference between JNJ-56136379+NA and placebo+NA) obtained in a Bayesian analysis. This Bayesian analysis will incorporate historical data for the placebo+NA arm(s) in an informative MAP prior with robustness modifier. For the current sample size simulations, historical data comes from an ongoing systematic literature review on HBsAg declines during NA treatment, resulting in 20 studies including around 2,835 subjects. More details on the eventual historical data, including all references to all studies, will be provided in the Modeling and Simulation

Report/SAP. For each study part and HBeAg status subgroup the appropriate historical prior will be used. Within Part A and Part B, JNJ-56136379+NA will also be compared with JNJ-56136379 as monotherapy but without including historical data as both arms include experimental treatments and appropriate historical data are consequently missing. In addition a similar analysis but without historical data in a frequentist approach will also be conducted as a sensitivity analysis.

The dose-response of JNJ-56136379 in an NA background regimen will be studied by a multiple contrast test (MCP) using 3 model-based contrasts covering the 3 possible shapes (linear, convex, and concave) with a control group (placebo+NA) and 2 doses. This analysis uses the data of these 3 treatment groups together to evaluate a dose-response signal, assuming a similar dose effect for each HBeAg subgroup and no difference in placebo+NA across Parts A and B. Sensitivity analyses will be done investigating differences across Parts A and B and differences between the two HBeAg subgroups.

### **11.3.2. Resistance Analyses**

The results of HBV viral sequencing will be evaluated by the sponsor virologist. Pretreatment amino acid and/or nucleic acid substitutions in the HBV pre-core and core regions and RT domain in all subjects and relevant changes in the HBV pre-core and core region and RT domain in subjects not responding to treatment tabulated and described. The effect of pretreatment HBV pre-core and core protein substitutions on efficacy will be evaluated.

Additional exploratory characterization of the HBV viral sequence and phenotype may be performed and reported separately.

### **11.3.3. Other Analyses**

Mean changes and maximum mean decrease from baseline in HBsAg, HBeAg, and HBV DNA levels over time will be tabulated by study treatment together with respective SDs. The proportion of subjects with seroclearance and seroconversion of HBsAg and HBeAg will also be tabulated by study treatment. The proportion of subjects with virologic response and the proportion of subjects with virologic or clinical relapse, defined as HBeAg, HBsAg, and/or HBV DNA levels below and above certain thresholds at different time points, respectively, will be categorized as detailed in the SAP, as applicable. Data will also be presented graphically by study phase, study treatment and by individual subject. All individual values will be presented in subject listings.

The least squares (LS) mean change from baseline in serologic parameters and HBV DNA for each study treatment and time point will be estimated with a repeated measurement model (mixed-effects model for repeated measures) including study treatment and time point as fixed effect. The model will allow for unequal variances between study treatments. A 95% confidence interval (CI) will be constructed around the difference between the LS mean of each study treatment. Other methods to evaluate the changes in serologic parameters and HBV DNA may include slope estimation, time-to-event or proportions of subjects who reach a certain level or who exceed a certain reduction.

The proportion of subjects with sustained reduction/suppression and/or sero-clearance, including but not limited to functional and partial cure, will be determined during follow-up. Single and multiple markers such as HBsAg, HBeAg, HBV DNA and ALT levels will be taken into consideration in this analysis.

Other efficacy endpoints, eg, HBV RNA and HBcrAg, will be analyzed descriptively. For continuous variables, descriptive statistics (n, mean, SD, median, minimum, maximum) will be calculated; mean difference and CIs may be calculated where appropriate and, if appropriate, a general linear mixed model will be used to compare the different study treatments. For categorical variables, frequency tables will be presented. Difference in proportions and CIs may be calculated where appropriate.

Analyses, tabulations and visualizations will be done for both treatment and follow-up phases.

#### **11.4. Pharmacokinetic Analyses**

Descriptive statistics (n, mean, SD, coefficient of variation, geometric mean, median, minimum, and maximum) will be calculated for the plasma concentrations of total JNJ-56136379 and/or NA (ETV or TDF), as applicable, and for the derived plasma and urine pharmacokinetic parameters.

For each subject, plasma concentration-time data of JNJ-56136379 and NA (ETV or TDF) will be graphically presented. Similarly, graphs of the mean plasma concentration-time profiles and overlay graphs with combined individual plasma concentration-time profiles will be produced. Pharmacokinetic parameters will be subjected to an exploratory graphical analysis, including various transformations, to get a general overview.

Actual and/or dose-normalized pharmacokinetic parameters will be graphically displayed for JNJ-56136379 and NA (ETV or TDF) when administered alone or in combination and as function of the dose to explore dose-linearity and dose-proportionality.

Predose plasma concentrations ( $C_{trough}$ ) at Weeks 1, 2, 4, 8, 12, 20, and 24 will be compared graphically to assess the achievement of steady-state concentrations and population PK predictions of JNJ-56136379 and NA (ETV or TDF), as applicable.  $C_{trough}$  at Weeks 28, 32, 36, 44 and 48 in the treatment extension phase will be compared with population PK predictions of JNJ-56136379 and NA, as applicable. Plasma concentrations of JNJ-56136379 and NA (ETV or TDF) at FU Weeks 2 and 4 will be determined to assess the elimination of JNJ-56136379 and NA after EOT.

The pharmacokinetic parameters of JNJ-56136379 and NA (ETV or TDF) at steady-state and on Day 1 (treatment with JNJ-56136379 after one dose) will be graphically displayed and descriptive statistics will be performed to determine the multiple dose pharmacokinetic (accumulation ratio) of JNJ-56136379 and NA (ETV or TDF). The pharmacokinetic parameters will be  $C_{max}$ ,  $C_{\tau}$ , and  $AUC_{\tau}$ .

Special attention will be paid to the plasma concentrations and pharmacokinetic parameters of those subjects who discontinued the study for an AE, or who experienced an AE  $\geq$ grade 3, or an SAE.

PopPK analysis of plasma concentration-time data of JNJ-56136379 will be performed using nonlinear mixed-effects modeling. Data may be combined with those of a selection of Phase 1 studies to support a relevant structural model. Available subject characteristics (eg, demographics, laboratory variables, genotypes) will be tested as potential covariates affecting pharmacokinetic parameters. Details will be given in a popPK analysis plan and results of the popPK analysis will be presented in a separate report.

### **11.5. Pharmacokinetic/Pharmacodynamic Analyses**

Relationships of pharmacokinetic parameters for JNJ-56136379 and NA (ETV or TDF) with selected efficacy and with selected safety endpoints will be evaluated and graphically displayed.

Modeling of key pharmacodynamic parameters (eg, HBsAg, HBV DNA) may be performed using population pharmacokinetics/pharmacodynamics (PK/PD). If PK/PD modeling of key efficacy endpoints is performed, possible covariates such as disease progression and/or treatment effect will be investigated. Other biomarkers may be explored at the sponsor's discretion. Details of the PK/PD analyses will be described in a population PK/PD analysis plan and results will be presented in a separate report.

### **11.6. Exploratory Pharmacokinetic Analysis of Hormonal Contraceptives**

Plasma concentrations of hormonal contraceptives and their metabolites will be summarized by study treatment and displayed graphically. The relationship between JNJ-56136379 exposure and hormonal contraceptive (parent and metabolite) exposure will be evaluated. Further exploration of pharmacokinetic interaction with hormonal contraceptive may be conducted in a physiological-based pharmacokinetics (PBPK) model. Population pharmacokinetics assessments for EE will be applied. Various generalized linear (mixed effects) models will be explored to evaluate the effect of JNJ-56136379 on the exposure of EE. If applied, the details of the PBPK and the population PK modeling approach and its results will be presented in a separate report.

### **11.7. Exploratory Biomarker Analysis**

Statistical approaches to explore correlations between clinical outcome and blood biomarkers vary and depend on the different data types of the applied technology platforms, as well as on the extent of observed differences between subjects. Analyses will be conducted at the sponsor's discretion, will always be under the sponsor's supervision, and results will be presented in the clinical study report or a separate report.

### **11.8. Pharmacogenomic (DNA) Analyses**

The statistical approach for analyzing the exploratory host DNA research may depend on the objective of the analyses (efficacy, safety, and pharmacokinetics) and possibly relevant genes at the time of analysis. Analyses will be conducted at the sponsor's discretion, will always be under

the sponsor's supervision, and results will be presented in the clinical study report or a separate report.

### **11.9. Patient-Reported Outcome Analyses**

PRO scores will be analyzed descriptively by study treatment as mean scores over time, and evaluated based on the proportion of subjects experiencing a clinically important improvement or worsening (if applicable) in PRO scores from baseline during the treatment phase and at the follow-up Week 12 visit (EQ-5D-5L and HQQOL) and follow-up Week 24 visit (MOS-CFS Cog-R and SF-36v2). In addition, effect sizes will be calculated to measure the magnitude of difference between means.

### **11.10. Safety Analyses**

All subjects who received at least 1 dose of study drug will be included in the safety analysis. Baseline is defined as the last assessment prior to the first study drug administration.

#### **Adverse Events**

The verbatim terms used in the eCRF by investigators to identify AEs will be coded using the Medical Dictionary for Regulatory Activities. Treatment-emergent AEs are AEs with onset during the treatment phase or that have worsened since baseline. For each AE (treatment-emergent and other), the percentage of subjects who experience at least 1 occurrence of the given event will be tabulated by study treatment. In addition, comparisons between treatment groups will be provided if appropriate.

Frequency tabulations, listings, datasets, or subject narratives may be provided, as appropriate, for those subjects who die, who discontinue treatment due to an AE, or who experience an AE of at least grade 2, at least possibly related, or an SAE.

For this study events of special interest (ESIs) are liver enzyme increases (eg, AST/ALT elevation). All ESIs will be listed in conjunction with other symptoms and laboratory abnormalities: eg, information on time of onset, duration of events, time to resolution, concomitant therapies, and relationship to study treatment.

#### **Clinical Laboratory Tests**

Laboratory data will be summarized by type of laboratory test. Descriptive statistics (n, mean, standard error [SE], SD, 95% CI, minimum, median, and maximum) of the actual values and changes from baseline per time point will be tabulated per treatment.

The laboratory abnormalities will be determined according to the criteria specified in the DAIDS Toxicity Grading Scale and in accordance with the normal ranges of the clinical laboratory if no gradings are available.

Based on current data review, for this study cholesterol increased is considered a laboratory abnormality of interest.

The percentage of the subjects who experience (worst) laboratory abnormalities will be tabulated by study treatment.

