A urine sample must be provided for urinalysis. Specific gravity, pH, glucose, protein, blood, ketones, bilirubin, urobilinogen, nitrite, and leukocyte esterase will be determined using dipstick. In case of positive dipstick results, the sediment will be examined microscopically for RBCs, WBCs, and epithelial cells and an additional examination will be performed on the positive urinary parameter (eg, quantification as applicable). Crystals, casts and bacteria will only be reported if they are present.

- At screening, a serum pregnancy test will be performed for women of childbearing potential.
- At screening, an FSH test will be performed for postmenopausal women.

- At time points as indicated in the **TIME AND EVENTS SCHEDULE**, a urine pregnancy test will be performed (women of childbearing potential only).
- At screening, a HIV-1 and -2 test, and hepatitis A, B, C, D, and E tests will be performed.
- At screening and time points as indicated in the **TIME AND EVENTS SCHEDULE**, tests will be performed for HBsAg, HBeAg, HBcAg, and anti-HBs and anti-HBe antibodies.
- At screening and time points as indicated in the **TIME AND EVENTS SCHEDULE**, determination of coagulation parameters will be performed. INR will be calculated by the central laboratory.
- At screening, alpha-fetoprotein will be measured.

In case of **rash**, blood samples (mandatory blood sample for safety in case of Grade 3 or Grade 4 rash and at the discretion of the investigator in case of Grade 1 or Grade 2 rash) need to be taken for safety laboratory testing, and are to be processed by the local laboratory. These samples need to be taken at unscheduled visits as described in [Attachment 3](#). The following parameters need to be tested: AST, ALT, erythrocyte sedimentation rate, creatinine, and a complete blood cell count (including hemoglobin, hematocrit, RBC count, WBC count, neutrophils, lymphocytes, monocytes, eosinophils, basophils, and platelet count).

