## **10.2. Discontinuation of Study Treatment/Withdrawal from the Study**

### **Discontinuation of Study Treatment**

A subject will not be automatically withdrawn from the study if he or she has to discontinue study treatment before the end of the 24- or 48 week treatment phase, as applicable.

A subject's JNJ-56136379 treatment must be discontinued and NA may be discontinued based on investigator judgement in consultation with the sponsor if:

1. The subject withdraws consent.
2. The investigator believes that for safety reasons or tolerability reasons (eg, AE) it is in the best interest of the subject to discontinue study treatment.
3. The subject becomes pregnant.
4. The subject has a  $\geq$  gradea 3 rash (see [Attachment 3](#)).
5. The subject has a  $\geq$  grade 3 allergic reaction, nausea, or diarrhea.
6. The subject has a grade 4 AE or confirmed laboratory abnormality (with the exception of ALT/AST elevations) considered at least possibly related to study drugs by the investigator.
7. The subject experiences a treatment-emergent elevation of ALT  $>2x$  baseline value, in combination with either direct bilirubin  $>1.2x$  ULN or INR  $>1.5x$  ULN or serum albumin  $<$  LLN, confirmed by retesting.
8. The subject has signs of hepatic decompensation (ie, clinical evidence of ascites, bleeding varices, or hepatic encephalopathy).
9. The subject has a confirmed  $\geq$  grade 3 serum creatinine abnormality, regardless of the relationship to the study drugs. In this case, JNJ-56136379 must be discontinued. The subject may continue ETV or switch from TDF to ETV at the investigator's discretion and enter follow-up.

Subjects who are receiving TDF and develop confirmed treatment-emergent  $\geq$  grade 3 abnormalities in urinalysis, considered at least possibly related to TDF, may switch to ETV and continue JNJ-56136379 for 4-8 weeks. If the urinalysis abnormality persists at the end of the 4-8 weeks NA switching phase, JNJ-56136379 must be discontinued. Subjects may continue NA treatment at the investigator's discretion and enter follow-up.

---

a Grades in this list are per the DAIDS Toxicity Grading Scale.

If the confirmed  $\geq$  grade 3 urinalysis abnormality is not considered at least possibly related to TDF or ETV, or any other concomitant disease and its medication, JNJ-56136379 must be discontinued. Subjects may continue NA treatment at the investigator's discretion and enter follow-up.

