**Table 6: Laboratory Parameters to Be Summarized**

Category	Abnormality	SDTM LBTESTCD	Grading system
General biochemistry	Alpha-1 Acid Glycoprotein	A1AGLP	Abnormalities
	Alpha Fetoprotein	AFP	Abnormalities
	Albumin	ALB	DAIDS
	Amylase	AMYLASE	DAIDS
	Amylase, Pancreatic	AMYLASEP	DAIDS
	Bicarbonate	BICARB	DAIDS
	Calcium	CA	DAIDS
	Creatine Kinase	CK	DAIDS
	Chloride	CL	Abnormalities
	Creatinine	CREAT	DAIDS
	C Reactive Protein	CRP	Abnormalities
	Follicle Stimulating Hormone	FSH	NAP
	GFR from Creatinine Adjusted for BSA	GFRBSCRT	DAIDS
	Choriogonadotropin Beta	HCG	NAP
	Potassium	K	DAIDS
	Lipase	LIPASET	DAIDS
	Magnesium	MG	DAIDS
	Phosphate	PHOS	DAIDS
	Protein	PROT	Abnormalities
	Sodium	SODIUM	DAIDS
Urate	URATE	DAIDS	
Urea Nitrogen	UREAN	Abnormalities	
General hematology	Hematocrit	HCT	Abnormalities

Hemoglobin	HGB	DAIDS	
Hypochromic RBC (RBC)	HPORBC	Abnormalities	
Mean Corpuscular hemoglobin	MCH	Abnormalities	
MCH concentration	MCHC	Abnormalities	
Mean Corpuscular volume	MCV	Abnormalities	
Platelet count	PLAT	DAIDS	
Erythrocytes	RBC	Abnormalities	
Leukocytes	WBC	DAIDS	
Hematology coagulation	Activated Partial Thromboplastin Time	APTT	DAIDS
	Fibrinogen	FIBRINO	DAIDS
	Prothrombin Intl. Normalized Ratio	INR	NAP
	Prothrombin Time	PT	DAIDS
Hematology different counts	Basophils	BASO	Abnormalities
	Basophils/Leukocytes	BASOLE	Abnormalities
	Eosinophils	EOS	Abnormalities
	Eosinophils/Leukocytes	EOSLE	Abnormalities
	Lymphocytes	LYM	Abnormalities
	Lymphocytes/Leukocytes	LYMLE	Abnormalities
	Monocytes	MONO	Abnormalities
	Monocytes/Leukocytes	MONOLE	Abnormalities
	Neutrophils and Precursors	NEUTPR	DAIDS
	Neutrophils, Segmented	NEUTSG	Abnormalities
	Neutrophils, Segmented/Leukocytes	NEUTSGLE	Abnormalities
Hepatic parameters	Alkaline phosphokinase	ALP	DAIDS
	Alanine Aminotransferase	ALT	DAIDS
	Aspartate Aminotransferase	AST	DAIDS
	Direct Bilirubin	BILDIR	Abnormalities
	Bilirubin	BILI	DAIDS
	Indirect Bilirubin	BILIND	Abnormalities
	Gamma glutamyl transferase	GGT	Abnormalities
	Lactate Dehydrogenase	LDH	Abnormalities
Lipids and glucose	Cholesterol	CHOL	DAIDS
	Glucose	GLUC	DAIDS
	HDL Cholesterol	HDL	Abnormalities
	LDL Cholesterol	LDL	DAIDS
	Triglycerides	TRIG	DAIDS
Urinalysis	Urine Pregnancy	HCG	NAP
	Protein	PROT	DAIDS
	Glucose	GLUC	DAIDS
	Bilirubin	BILI	Abnormalities
	pH	PH	Abnormalities

	Specific Gravity	SPGRAV	Abnormalities
	Ketones	KETONES	Abnormalities
	Urobilinogen	UROBIL	NAP
	Nitrite	NITRITE	Abnormalities
	Leukocyte Esterase	LEUKASE	Abnormalities

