### Toxicity grades and abnormalities for laboratory parameters:

The laboratory abnormalities will be determined according to the criteria specified in the Division of AIDS (DAIDS) Toxicity Grading Scale. In case different grades are available for fasted/non-fasted results, the results are assumed to be taken in the condition as specified in the protocol (i.e. not necessarily according to possible remarks indicating a deviation to this). In case no toxicity grades are defined for a laboratory test, then non-graded abnormalities (high/low vs. normal range) will be used. The tests with toxicity grades and abnormalities have been summarized in table 6. Toxicity grades according to DAIDS will be derived for urinary protein and urinary glucose although these are categorical test (see table 7).

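### SAP Table 6 marks the grading of INR as not applicable, which contradicts SAP 6.2 and protocol 11.10 and, if followed, removes INR from every by-arm abnormality table

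*Protocol*

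**What the plan says.** Protocol 11.10 (Clinical Laboratory Tests) sets a two-step rule. Abnormalities are determined by the DAIDS Toxicity Grading Scale and "in accordance with the normal ranges of the clinical laboratory if no gradings are available". The required output follows: "The percentage of the subjects who experience (worst) laboratory abnormalities will be tabulated by study treatment". No test is exempted.

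INR is a planned result. Protocol 9.9 schedules coagulation parameters at screening and at the visits in the Time and Events Schedule, and states that "INR will be calculated by the central laboratory".

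INR also has a role in subject safety. Protocol 10.2, criterion 7, concerns a treatment-emergent ALT above 2x baseline "in combination with either direct bilirubin" above 1.2x ULN, INR above 1.5x ULN, or serum albumin below LLN, confirmed by retesting. The same INR limit is an entry exclusion for hepatic decompensation (Protocol 4.2, criterion 3).

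The SAP says two different things. Its text in 6.2 gives the protocol's fallback: "In case no toxicity grades are defined for a laboratory test, then non-graded abnormalities (high/low vs. normal range) will be used". Its Table 6, in the coagulation block, has the row "Prothrombin Intl. Normalized Ratio INR NAP". The SAP's abbreviation list defines NAP as not applicable.

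**The concern.** A not-applicable entry is not the code that the SAP uses for a test without a toxicity grade. For those tests Table 6 uses *Abnormalities*, meaning high or low against the normal range. The NAP entry therefore takes INR out of both branches of the rule that the protocol and the SAP text share.

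Liver enzyme increases are the trial's events of special interest, and INR is the synthetic-function measure that criterion 7 pairs with an ALT rise. If INR is never classified, the report will not state how many subjects in each arm had an abnormal INR or one that worsened from baseline. The protocol asks for that type of safety table for every laboratory test.

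**Working it through.** No sample size, alpha or event count is involved, so there is nothing to compute. The check sets the relevant texts side by side.

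**1. Which code Table 6 assigns.**

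| Test | Table 6 block | Grading system |
|---|---|---|
| APTT | Coagulation | DAIDS |
| Fibrinogen | Coagulation | DAIDS |
| Prothrombin time | Coagulation | DAIDS |
| INR | Coagulation | NAP |
| Direct bilirubin | Hepatic | Abnormalities |
| Albumin | General biochemistry | DAIDS |

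INR is the only NAP entry among the coagulation tests. The others in Table 6 are FSH, serum HCG, urine pregnancy and urobilinogen, and none of those has a numerical limit in protocol 10.2. Of the three alternatives that accompany the ALT rise in criterion 7, direct bilirubin and albumin are classified and INR is not.

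**2. What depends on the code.** SAP 6.2 says that Table 6 summarises which tests carry grades or abnormalities. It then creates a worst-case record only for parameters with a defined grade or abnormality. The later outputs use those classifications: cross-tabulations of worst grade or abnormality against baseline, tables of treatment-emergent worst grades and abnormalities, and listings triggered by a treatment-emergent finding. With NAP, INR has no row in any of these.

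**3. The hepatic listing.** This listing shows all hepatic parameters for subjects with a treatment-emergent hepatic finding. INR and albumin sit outside the Table 6 hepatic block, so neither is shown there.

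**4. What remains for INR.** SAP 6.2 plans descriptive statistics of values and changes per parameter over time. SAP 2.6 includes minimum, median and maximum among them. SAP 6.2 also plans plots of actual values with one line per subject. Under SAP 2.3, summaries per time point and graphics use one selected value per visit window, whereas the worst-case record includes unscheduled assessments. The remaining outputs are therefore not a full substitute where a raised INR comes from a retest.

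**5. How much data is affected.** Coagulation is scheduled at Weeks 1, 2, 4, 8, 12, 16, 20 and 24 (8 visits) and at Weeks 28, 32, 36, 40, 44 and 48 (6 visits). That gives 8 + 6 = 14 post-baseline treatment visits for a subject who enters the extension. This is a count of visits and does not show that any signal would be lost.

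**The case against.** The strongest reply is that the SAP has not decided to leave INR unclassified. The general sentence in 6.2 would give INR a high/low flag if applied, and nothing states that Table 6 takes precedence. That is correct, and it makes the defect an internal contradiction. It still has to be resolved, because a programmer is likely to work from the test-specific table.

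A reader might infer that INR would be visible only as group means. The documents do not support that: minimum, maximum and individual-subject plots are planned. None of these compares values with the ULN or counts subjects by arm.

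Prothrombin time comes from the same panel, is DAIDS-graded and will have worst-grade, shift and treatment-emergent tables. Related information is therefore present. Criterion 7 and the entry exclusion are nevertheless written in INR.

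A reader might also infer that subjects who stop under criterion 7 would go unseen. That does not follow. Study-agent discontinuations are tabulated by reason and listed (SAP 4.1), clinically relevant laboratory changes are to be recorded as AEs (Protocol 9.9), and TEAEs leading to discontinuation and events of special interest have their own tables (SAP 6.1). INR also counts under criterion 7 only together with the ALT rise.

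Finally, correcting the cell would not count subjects above 1.5x ULN, because a normal-range flag marks any value outside the range. The same limitation applies to the planned direct bilirubin table and its 1.2x ULN limit. This objection stands, and it is why a criterion 7 table is an optional addition.

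**Conclusion.** The point holds as a contradiction with a definite consequence. Table 6 disagrees with the text of SAP 6.2 and with protocol 11.10. If Table 6 is followed, INR has no worst-case record, no shift table, no treatment-emergent table and no abnormality-triggered listing. The loss is confined to the INR-specific abnormality counts by arm; descriptive statistics, individual plots and graded prothrombin time remain.

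The conclusion assumes that programming follows the test-specific table over the general sentence. It does not depend on whether the DAIDS scale grades INR. The scale is not reproduced in the documents, so that was not judged, but both the protocol and the SAP text call for a classification either way. The study is exploratory and no efficacy conclusion is affected. The correction is still worth making, because it restores a safety tabulation that the protocol requires, at almost no cost.

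**What to change.** In SAP Table 6, replace NAP for INR with DAIDS if the cited version of the scale grades it, and otherwise with *Abnormalities* (normal range). Table 6 then agrees with the text of SAP 6.2 and with protocol 11.10, and INR enters the existing worst-case, shift and treatment-emergent outputs without further specification.

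Two additions are optional and not required by the protocol:

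- Show INR and albumin in the hepatic-parameter listing, beside ALT and bilirubin.
- Tabulate by arm and analysis phase the subjects who meet criterion 7 exactly as protocol 10.2 already defines it. The normal-range flag alone does not identify INR above 1.5x ULN or the combination with ALT.

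The required change is one table cell. The additions are two extra columns in a listing and one table. The central-laboratory data are already collected, and no clinical rule changes.
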